The current standard of care in patients who progress on PD-1 therapy alone is single-agent CTLA-4 inhibitor therapy (e.g. ipilimumab), despite lack of currently available prospective data in this setting. Historical response rates to ipilimumab as a single agent have been approximately 10%, and this includes first-line studies with ipilimumab, which could be expected to have a higher response rate than in the second line after failure of immunotherapy. (21,22,23) Additionally, one retrospective case series has reported a response to single-agent ipilimumab of 10% following single-agent nivolumab (PD-1 inhibitor) among 40 patients. (24) A clear benefit over the expected background rate of 10% response to ipilimumab alone would provide important preliminary data in the development of a synergistic effect between the combination even after failure of PD-1 therapy alone, and would have potential clinical utility in guidance of physicians and patients in choice of

upfront combinatorial approaches versus combination immunotherapy after failure of single-agent immunotherapy.

Our main hypothesis, therefore, is that patients with advanced melanoma who progress on anti-PD-1 therapy upfront may ultimately respond to the addition of the CTLA-4 inhibitor ipilimumab to continued PD-1 inhibition (with nivolumab), and that disease control (as measured using PFS) would be longer than that seen with switching to ipilimumab alone. We surmise that this would occur because melanomas primarily refractory to PD-1 antibodies may not have a preexisting T cell infiltrate, which can be corrected by adding treatment with the anti-CTLA-4 antibody ipilimumab. CTLA-4 blockade therapy acts at the activation step of an immune response and allows T cells to expand, circulate and infiltrate tumors, where they become negatively regulated by anti-PD-1. By adding CTLA-4 blockade to continued PD-1 blockade we hypothesize that T cells will infiltrate metastatic lesions and be able to induce their specific antitumor cytotoxic response by having released these two major immune checkpoints.

Translational Medicine

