11.0 STATISTICAL CONSIDERATIONS

11.1 Accrual Goal

Although the primary objective aims to assess whether combination therapy ipilimumab and nivolumab is superior to single therapy ipilimumab in patients who have previously progressed on anti-PD-1 or anti-PD-L1 therapy, major additional objectives of this study include assessment of key biomarkers and genomic correlatives, particularly for patients who receive combination therapy. This study will use a design in which 63 patients will be randomized to receive combination therapy ipilimumab and nivolumab and 21 patients will be randomized to receive single therapy ipilimumab. Assuming an ineligibility rate of 10% the total accrual goal is 94 patients.

The unbalanced randomization is motivated by the necessity of evaluating the first secondary objective. In particular, the underlying rationale for the combination therapy is that initial progression on PD-1 blockade alone results from poor T cell recruitment. If the combination therapy is superior to single agent ipilimumab, evaluation of this hypothesis by comparing T cell infiltration between patients who have an objective response (confirmed and unconfirmed partial or complete response per RECIST 1.1) and patients who do not have an objective response to combination therapy will elucidate mechanisms that are imperative for design and development of further studies of combination therapy in this population. Thus, unbalanced randomization is necessary to ensure adequate sample size for evaluating this hypothesis. Assuming a response rate of 25% and 90% compliance in tissue and biopsy submission, then we anticipate accruing 14 eligible objective responders and 43 eligible objective non-responders in the combination therapy arm.

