11.3 Secondary Objectives

An important hypothesis underlying the rationale for the combination therapy is that initial progression on PD-1 blockade alone results from poor T cell recruitment. Consequently, our first secondary endpoint will evaluate this by comparing the quantitative CD8+ expression levels between patients who eventually respond and patients who do not respond using a two-sample t-test and control the type I error at the two-sided 0.05 level. Assuming that the trial accrues to completion, 90% compliance in tissue and biopsy

submission, there will be 56 patients to evaluate this hypothesis. If it is further assumed that 25% of these patients respond, then we anticipate 80% power to detect a mean difference in CD8+ expression of 0.875 standard deviations. Evaluation of this hypothesis motivates the unbalanced randomization.

For the additional secondary objectives, the study will estimate the response rate (confirmed and unconfirmed, complete and partial responses) in each arm and construct 95% binomial confidence intervals. All randomized patients will be included in the analysis of response. Patients who cannot have their exact response determined due to inadequate disease assessments will be counted in the denominator as non-responders.

We will also construct Kaplan-Meier plots and estimate the median Overall Survival (OS) and construct 95% Brookmeyer-Crowley Confidence intervals. We will be able to estimate the ORR or the OS rates at a particular time point (e.g. 13 weeks) to within 12.3% (95% confidence interval (CI)) and 21.4% in the combination therapy and ipilimumab alone arms, respectively. Waterfall plots will be constructed to represent each patient's best change in tumor burden.

Toxicity will be assessed in each arm separately. Any toxicity with at least 5% chance of occurring has 93.7% and 60.3% chance of being observed at least once in the combination therapy and ipilimumab alone arms, respectively. We will be able to estimate the rate of occurrence of any particular toxicity to within 12.3% (95% CI) and 21.4% in the combination therapy and ipilimumab alone arms, respectively.

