Although our primary analysis will focus on developing classification models, we will also assess the association between response and each individual marker, clonality, mutational load, mRNA expression signature, and ctDNA fraction. The analysis will be again conducted separately by treatment arm. For each of the IHC markers, clonality, and ctDNA fraction, we will test for difference in mean levels between responders and non-responders using two-sample t-tests. We assume we obtain data on 90% of patients and that the response rates are 15% and 30% in arms 1 and 2, respectively. Then at the nominal $\alpha=0.05$ level, we anticipate 80% power to detect a difference in marker level, clonality, or ctDNA fraction between responders and non-responders of 1.9 and 0.83 standard deviations in Arms 1 and 2, respectively. Further, we will also assess whether individual mRNA transcripts and genes are associated with response. Specifically, we will compare the expression between patients who respond and who do not respond using two-sample t-tests again. We will accommodate multiple testing by controlling the false discovery rate. With the same response rate and sample size assumptions as before, and further assuming that 80% of genes are not associated with response, then at the FDR = 5% level, we anticipate 80% power to detect a difference in expression level of 2.43 and 1.33 standard deviations in Arms 1 and 2, respectively. Note that t-tests are used since they can be more powerful than logistic regression, but for all association analyses in this objective and subsequent translational medicine objectives, we will consider the use of alternative approaches, e.g. data transformation, Wilcoxon tests or logistic regression, if there are outliers or influential points.

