Since mutational load is far from normally distributed, we will use a Wilcoxon test to test for difference in mutational burden. To assess power, we conducted simulations under the assumption that we will collect exome sequencing data on 90% of patients and that we will control the type I error rate at the two-sided $\alpha=0.05$ level. To simulate mutational load, we used an internal, private data exome sequencing data set comprised of 13 non-responder patients to first line anti-PD1 therapy and sampled from the interpolated empirical cumulative distribution function (ECDF) via the inverse probability integral transform. For power analyses, data from this distribution were taken to be null. To simulate under the alternative, we shifted all of the mutational load values by a scalar δ and re-sampled from the interpolated ECDF of the shifted data. For Arm 1, assuming response rate of 15%, with 18 total patients, we anticipate 80% power to detect a shift in mutational load distribution of $\delta=13.9$. For Arm 2, assuming response rate of 30%, with 54 total patients, we anticipate 80% power to detect a shift in mutational load distribution of $\delta=2.7$. We again emphasize that alternative approaches will be considered if Wilcoxon tests do not perform well, e.g. due to heteroscedasticity etc.

2. **Objective 2:** Prognostic Value of T-cell Density, TCR Clonality, and Mutational Load

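### Section 18.1c plans the combination arm at a 30% response rate where Sections 11.1 and 11.3 use 25%, so the plan prints two detectable differences (0.83 and 0.875 SD) for the same kind of test

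*Combined protocol and SAP*

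**What the plan says.** **Arm 2 (combination).** Section 11.1 derives its expected numbers of responders and non-responders as follows: "Assuming a response rate of 25% and 90% compliance in tissue and biopsy submission". This gives 14 responders and 43 non-responders out of 63 patients. Section 11.3 repeats 25% for the CD8+ comparison, made "using a two-sample t-test and control the type I error at the two-sided 0.05 level", and concludes: "we anticipate 80% power to detect a mean difference in CD8+ expression of 0.875 standard deviations".

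Section 18.1c, Objective 1, then compares marker level, clonality and ctDNA fraction between responders and non-responders within each arm, again by two-sample t-test. Its premise is: "We assume we obtain data on 90% of patients and that the response rates are 15% and 30% in arms 1 and 2, respectively". At nominal alpha 0.05 and 80% power it gives differences between "responders and non-responders of 1.9 and 0.83 standard deviations in Arms 1 and 2, respectively". The mutational-load simulations in the same section reuse 30% for Arm 2 and 15% for Arm 1.

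**Arm 1 (ipilimumab alone).** Section 11 states no response rate. The Background describes about 10% as the historical rate and writes: "A clear benefit over the expected background rate of 10% response to ipilimumab alone". It adds that first-line studies, which contribute to that figure, could be expected to show higher response than treatment after failed immunotherapy.

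**mRNA.** With the same response rates and sample sizes, 80% of genes null and FDR 5%, Section 18.1c gives 2.43 SD in Arm 1 and 1.33 SD in Arm 2.

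**The concern.** The proportion of Arm 2 patients who respond is a single quantity in this trial, and it sets how unequal the two compared groups are. Planning it at 25% in one section and 30% in another yields two detectable differences for the same arm, availability, type of test and power. A reader cannot tell which describes the trial, and the one in Section 18.1c is the more favourable.

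This matters because Section 11.1 counts biomarker and genomic assessment among the study's major additional objectives and justifies the 3:1 randomization by the number of Arm 2 responders. Patients undergo research biopsies for this work, so its stated power should rest on the rate used to justify the design. In Arm 1 the issue is weaker: 15% is used without a source and is above the rate that the Background leads the reader to expect.

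**Working it through.** **Inputs.** Arm sizes are 63 and 21 (Section 11.1). Availability is 90%, so 63 × 0.9 = 56.7 and 21 × 0.9 = 18.9 patients with data. Alpha is 0.05. Section 18.1c gives no sidedness for these t-tests. Two-sided is assumed, as in Section 11.3; one-sided does not fit, giving about 0.73 and 1.67 SD.

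**Method.** For a difference of d standard deviations and group sizes n1 and n2, the noncentrality is d × √(n1·n2/(n1+n2)), with n1+n2−2 degrees of freedom. Power is the probability that this noncentral t exceeds the two-sided critical value.

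**Step 1: reproduce the plan's t-test figures.**

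| Arm, rate | Groups | √(n1·n2/(n1+n2)) | Difference at 80% power | Plan |
|---|---|---|---|---|
| Arm 2, 30% | 17.01 v 39.69 | 3.451 | 0.827 SD | 0.83 (18.1c) |
| Arm 2, 25% | 14.175 v 42.525 | 3.261 | 0.875 SD | 0.875 (11.3) |
| Arm 1, 15% | 2.835 v 16.065 | 1.552 | 1.92 SD | 1.9 (18.1c) |

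With whole patients, 3 v 15 in Arm 1 gives 1.89 SD. All three printed figures reproduce. In Arm 2 the response rate alone accounts for the gap between 0.83 and 0.875.

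**Step 2: Arm 2 power at 0.83 SD if 25% respond.**
- 14.175 v 42.525: noncentrality 0.83 × 3.261 = 2.71, power 75.8%.
- 14 v 43, the split in Section 11.1: √(14·43/57) = 3.250, noncentrality 2.70, power 75.5%. The difference detectable at 80% power is 0.877 SD.
- 14 v 42, the 56 patients of Section 11.3: power 75.2%, detectable difference 0.88 SD.

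**Step 3: Arm 1 sensitivity at 10%.** The expected number of responders falls from 18.9 × 0.15 = 2.8 to 18.9 × 0.10 = 1.9.
- 1.89 v 17.01: detectable difference 2.28 SD, power at 1.9 SD 64.6%.
- 2 v 17: 2.22 SD, power 66.9%.
- 2 v 16: 2.24 SD, power 66.3%.

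**Step 4: mRNA at FDR 5%.** With 80% of genes null and 80% power, the per-test alpha is 0.05 × 0.2 × 0.8 / (0.8 × 0.95) = 0.0105.
- Arm 1 at 15% (2.835 v 16.065): 2.43 SD, matching the plan.
- Arm 1 at 10%: 2.82 SD (2 v 17) to 2.89 SD (1.89 v 17.01). Power at 2.43 SD is 62-65%.
- Arm 2 at 30% (17.01 v 39.69): 1.02 SD. At 25% (14 v 43): 1.08 SD. The plan prints 1.33 SD, at which power would be about 97% and 95%.

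The Arm 2 mRNA figure therefore does not follow from the method that reproduces Arm 1, and it errs on the cautious side.

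**Not checked.** The mutational-load shifts come from a private dataset of 13 patients, so they cannot be rerun here.

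**The case against.** **The two Arm 2 figures serve different analyses.** Section 11.3 powers the first secondary objective, which Section 1.2 ties to on-study biopsies. Section 18.1c concerns baseline markers. Each states its assumption openly. This is true, but both split the same arm by response, so the timing of the biopsy gives no reason for a different response rate. Nor does a wider definition of response: the 25% in Section 11.1 already counts confirmed and unconfirmed responses.

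**A reader might infer that the printed figures are miscalculated.** They are not: 0.83, 1.9 and 2.43 SD all follow from their stated inputs.

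**A reader might infer that Arm 1 contains the same contradiction, 15% against 10%.** The documents do not support this. The 10% appears only in the Background, as a historical and expected background rate, and no calculation uses it. The Background does not say whether it counts unconfirmed responses. The 15% is the only Arm 1 rate in any power calculation, and "For Arm 1, assuming response rate of 15" per cent is stated openly a second time for mutational load. What stands is that 15% has no source and lies above the document's own expectation.

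**A reader might infer that the translational power is too favourable throughout.** The Arm 2 mRNA figure goes the other way.

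**The consequence is small.** Section 18.1c makes classification models its main analysis, and the precision stated for them (13.0% and 22.5%) does not depend on the response rate. The t-tests are supplementary. This stands and limits the weight of the point.

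**Conclusion.** The point holds for Arm 2 as an internal inconsistency in a planning assumption. At the 25% used in Sections 11.1 and 11.3, the Section 18.1c t-tests have 80% power at about 0.875-0.88 SD. At the stated 0.83 SD their power is about 75-76%, a loss of 4 to 5 percentage points. This rests on a two-sided test, 90% availability and normal-theory t-test power.

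For Arm 1 the finding is only that 15% is unsupported. The figures of 2.2-2.3 SD and, for mRNA, 2.8-2.9 SD are a sensitivity case at 10%, not a correction. The Arm 2 mutational-load power rests on the same 30%, but the size of any change there is unknown. The Arm 2 mRNA figure of 1.33 SD needs a separate check.

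The effect is confined to the translational power statements. The PFS sizing in Section 11.2, the accrual goal and the CD8+ power in Section 11.3 are unaffected.

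**What to change.** - **Arm 2:** use 25% throughout. In Section 18.1c restate 0.83 as about 0.875 SD and rerun the mutational-load simulation at 25%. The 30% may stay beside it, labelled as an optimistic scenario.
- **Arm 1:** give the source of 15% and show 10% as a sensitivity case: about 2.2-2.3 SD against 1.9 and, for mRNA, about 2.8-2.9 SD against 2.43.
- **Arm 2 mRNA:** recheck 1.33 SD. Either restate it (about 1.08 SD at 25%) or give the extra assumption behind it.
- **While restating:** settle one analysable number for Arm 2. Section 11.1 implies 14 + 43 = 57, Section 11.3 says 56, and the mutational-load text says 54.

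The cost is one simulation rerun and a few restated sentences. The sample size, the tests and the decision rules stay as they are, and the Arm 2 t-test figure becomes slightly less favourable.

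### The Arm 1 biomarker power in Section 18.1c appears to hold only at the expected split of about 3 responders; averaged over the random responder count, the t-test has about 70% power, not 80%

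*Combined protocol and SAP*

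**What the plan says.** Section 18.1c, Objective 1, analyses each arm separately and tests each marker between responders and non-responders. For the t-tests on IHC markers, clonality and ctDNA fraction, the assumptions are: "We assume we obtain data on 90% of patients and that the response rates are 15% and 30% in arms 1 and 2, respectively". At a nominal 0.05 level, the difference detectable with 80% power is then given as "between responders and non-responders of 1.9 and 0.83 standard deviations in Arms 1 and 2, respectively". A companion figure for individual mRNA transcripts, controlled by false discovery rate, is 2.43 SD in Arm 1.

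For mutational load the test is Wilcoxon, and "we will control the type I error rate at the two-sided $\alpha=0.05$ level". The power was simulated: "To assess power, we conducted simulations under the assumption that we will collect exome sequencing data on 90% of patients". The source was "an internal, private data exome sequencing data set comprised of 13 non-responder patients", and the alternative was a shift of that distribution. The result is: "For Arm 1, assuming response rate of 15%, with 18 total patients, we anticipate 80% power to detect a shift in mutational load distribution", with delta = 13.9.

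The section does not give the number of responders used, whether that number was fixed or drawn at random, or what is done with 0 or 1 responder.

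**The concern.** Responder and non-responder groups are formed by outcome, so their sizes are not set by design. With 18 or 19 patients and a 15% rate, the expected number of responders is below 3, and the count varies widely around that. Power at the expected split is then a poor guide to the power that the analysis will have, because power falls quickly below 3 responders and rises only slowly above it. With 0 responders there is no test, and with 1 the Wilcoxon test cannot be significant at 5%.

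What is at stake is the reading of a non-significant Arm 1 marker. Against a stated 80% power, it could be taken as fair evidence that the marker does not separate responders on ipilimumab alone, when about one Arm 1 dataset in five could not give a significant Wilcoxon result at all.

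**Working it through.** **Inputs.** Arm 1 has 21 patients (Section 11.1). With 90% availability, 21 x 0.9 = 18.9; the mutational-load statement prints 18. The Arm 1 response rate is 15% (Section 18.1c). The Wilcoxon test is two-sided at 0.05 (Section 18.1c). The sidedness of the t-test is not printed; I take two-sided 0.05 with pooled variance, because that reproduces the plan's figure.

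**Step 1: the plan's own t-test figure.** With r responders and n - r non-responders, power at a difference of d SD comes from the noncentral t with n - 2 degrees of freedom and noncentrality d x sqrt(r(n - r)/n). At d = 1.9:

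| Split | Power at 1.9 SD | SD needed for 80% |
|---|---|---|
| 3 v 15 | 80.5% | 1.89 |
| 3 v 16 | 81.2% | 1.87 |
| 2.835 v 16.065 (unrounded, 18.9 x 0.15) | 79.3% | 1.92 |

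Each detectable difference rounds to the printed 1.9. The plan's figure is reproduced by the expected split, whether rounded or not.

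**Step 2: distribution of the responder count.** Let R be Binomial(n, 0.15).

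- n = 18: P(R = 0) = 0.85^18 = 5.4%; P(R = 1) = 18 x 0.15 x 0.85^17 = 17.0%; together 22.4%.
- n = 19: 4.6% and 15.3%; together 19.8%.

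Exactly 3 responders has a probability of only 24% at either n.

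**Step 3: Wilcoxon ceiling.** If all r responders rank above everyone else, the exact two-sided p is 2/C(18, r).

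- r = 1: 2/18 = 0.111, so rejection at 5% is impossible. The normal approximation gives 0.101, or 0.123 with continuity correction, so the conclusion is the same.
- r = 2: 2/153 = 0.013, so rejection is possible.

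Power averaged over R therefore cannot exceed P(R >= 2), whatever the shift or the shape of the private data:

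- n = 18: 1 - 0.224 = 77.6%.
- n = 19: 80.2%.
- n = 18, discarding datasets with no responder: 0.776/0.946 = 82.0%.

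These are upper limits. Power at delta = 13.9 itself cannot be checked, because the 13-patient distribution is not in the documents.

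**Step 4: t-test power averaged over R, n = 18, d = 1.9.**

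| r | P(R = r) | Power | Product |
|---|---|---|---|
| 0 | 0.054 | 0 (no test) | 0 |
| 1 | 0.170 | 0.411 | 0.070 |
| 2 | 0.256 | 0.663 | 0.169 |
| 3 | 0.241 | 0.805 | 0.194 |
| 4 | 0.159 | 0.882 | 0.140 |
| 5 | 0.079 | 0.923 | 0.073 |
| 6 | 0.030 | 0.946 | 0.028 |
| 7 | 0.009 | 0.958 | 0.009 |

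With the small remaining terms the sum is 68.6%; a simulation gave 68.7%. At n = 19 it is 71.1%. Average power of 80% needs 2.30 SD (n = 18) or 2.20 SD (n = 19).

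**Step 5: Arm 2 for comparison.** At 0.83 SD and a 30% rate, 17 v 39 gives 80.1%, which reproduces the print. Averaged over the binomial count, power is 77.1% (n = 54) to 79.4% (n = 57). The loss is 1 to 3 points, against 9 to 11 in Arm 1.

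**mRNA figure.** I give no corrected value. The per-test alpha is not printed. A standard conversion (5% FDR, 80% null genes, 80% power) gives 0.05 x 0.2 x 0.8/(0.95 x 0.8) = 0.0105. That reproduces the Arm 1 figure at the unrounded split (2.43 SD), but it gives about 1.01 to 1.05 SD in Arm 2 against the printed 1.33. The sponsor's own alpha is needed.

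**The case against.** The strongest reply is that nothing was miscalculated. The section states its assumed response rates, power at the expected split is ordinary planning practice, and the t-test figure reproduces. This stands as a description of what was done. It does not rescue the figure: the shortcut costs little in Arm 2, but in Arm 1 it overstates the power by about 9 to 11 points.

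A reader might infer more than the documents support:

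- *That all the Arm 1 figures come from a closed calculation with exactly 3 responders.* The mutational-load power was simulated and no responder count is printed. Unrounded expected counts also give 1.9 SD. A fixed count in the simulation is an inference.
- *That the Wilcoxon test can never reach 80%.* This is true at the printed 18 patients with responder-free datasets counted as failures. The ceiling is just above 80% at n = 19, and 82.0% at n = 18 if those datasets are dropped. The section does not say that they were dropped; if they were, the 80% is conditional and should be labelled so.
- *That the true Wilcoxon power at delta = 13.9 is some particular lower value.* That would require assuming a shape for the private data.

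Two further replies have partial force. The section allows alternative methods if the planned tests behave poorly, but it mentions outliers, influential points and heteroscedasticity, not too few responders. And these are association tests that the section itself ranks below the classification models. That limits the importance of the point. Nor does the plan say that a null Arm 1 result will be read as absence of effect; that is a risk of interpretation.

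**Conclusion.** The concern holds in a limited form. The Arm 1 power figures in Section 18.1c appear to be conditional on about 3 responders. Averaged over the responder count at the plan's own 15% rate, the t-test at 1.9 SD has 69% to 71% power rather than 80%. With the 18 patients printed for mutational load, Wilcoxon power is at most 77.6%, against the stated 80%.

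The t-test result assumes a two-sided 5% level, pooled variance, normal data and zero-responder datasets counted as non-significant; the shortfall remains at either n. The Wilcoxon excess over the ceiling is small (2.4 points) and depends on n = 18 and on how responder-free datasets are counted. The more useful Wilcoxon statement is the 20% to 22% chance that no significant result is possible. The point is confined to secondary translational analyses, mainly in Arm 1. The primary PFS comparison is unaffected.

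**What to change.** In Section 18.1c, Objective 1:

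1. For the Arm 1 t-tests, print about 70% power at 1.9 SD, or 80% power at 2.2 to 2.3 SD, and say that the figure is averaged over a binomial responder count.
2. Rerun the existing mutational-load simulation with a binomial responder count at one stated n (18 or 19). Count datasets with 0 or 1 responder as non-significant, and print the resulting power at delta = 13.9.
3. Recompute the Arm 1 mRNA figure at 2.43 SD in the same way, with the sponsor's own per-test alpha, and print that alpha.
4. State that Arm 1 marker tests are reported descriptively if there are fewer than 2 responders.

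The cost is a wording change, one rerun of a simulation that already exists and one recalculation. Patients, data collection and the primary analysis do not change. The downside is that the stated Arm 1 figures become less favourable.
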